#### **1.2.3.1. Radiotoxicity of Omburtamab Labels Other Than Lutetium-177**

A non-GLP study was conducted to evaluate radiotoxicity of I-omburtamab in 2 male cynomolgus monkeys given multiple doses of 3.62 to 8.3 mCi I-omburtamab via intrathecal injection. One monkey was preimmunized with I-omburtamab by IV administration 210 and 127 days prior to study initiation to evaluate anti-drug antibody (ADA) generation.

I-omburtamab produced detectable spikes of I-omburtamab in the CSF and comparatively lower levels of radiation in the blood. Suppressed levels in the blood of the preimmunized animal were likely due to a monkey anti-mouse antibody response that did not affect levels measured in the CSF. In general, total radioactivity elimination from the CNS was nearly complete by 48 hours post dose. I-omburtamab was tolerable for nontraumatic cisternal puncture. The findings associated with dosing, including changes in laboratory values measured in the CSF and blood, were transient and reversible. Beyond the injection site, no significant gross pathology or histopathological findings were noted in either animal and no long-term toxicities were observed after extended follow-up (i.e., >1200 days after the last dose).

Single-dose studies with the monoclonal antibody have been conducted for biotinylated omburtamab, I-omburtamab, and I-omburtamab in xenografted mice, naïve rats, or monkeys. The test agents were administered via IV or intratumoral infusions for mice, intraparenchymal infusion or convection-enhanced delivery for rats, and convection-enhanced delivery for monkeys. There was no evidence of neurological toxicity with biotinylated omburtamab. The radiolabeled antibodies were well tolerated in mice, rats, and monkeys at radioactivity doses up to 500 µCi I-omburtamab or 1 mCi I-omburtamab, the highest levels of radioactivity evaluated.

#### 1.2.4. Preclinical Pharmacokinetics of Lu-DTPA-omburtamab

Electrochemiluminescence assays were developed and validated to support quantification of DTPA-omburtamab in plasma and CSF from cynomolgus monkey.

No standalone pharmacokinetic (PK) studies have been conducted with Lu-DTPA-omburtamab. Toxicokinetic parameters were determined in juvenile monkeys given a single intracerebroventricular infusion of vehicle or DTPA-omburtamab (CAR 1). The no-observed-adverse-effect level (NOAEL) of 1.5 mg/kg DTPA-omburtamab corresponded to a maximum observed drug concentration (Cmax) of 18,200 ng/mL total omburtamab and a mean area under the concentration-time curve (AUC) from time 0 to 672 hours of 1,350,000 hr·ng/mL and AUC from time 0 to infinity of 1,300,000 hr·ng/mL. There were no sex differences in toxicokinetic parameters. Total omburtamab was detectable in plasma at 1 hour post dose. Maximum plasma concentration and AUC increased with increasing dose in a greater than dose proportional manner. Time to maximum concentration was 12 hours and half-life was 23.9 to 26.1 hours. Mean clearance and volume of distribution of total omburtamab decreased with increasing dose. Total omburtamab was detectable in CSF in all dose groups at 24 hours post dose, and below the limit of quantification on Day 30. Concentrations were dose proportional for 0.1 and 0.75 mg/kg DTPA-omburtamab. There was no further increase in CSF levels at 24 hours post dose for 1.5 mg/kg compared to 0.75 mg/kg.

Biodistribution of Lu-DTPA-omburtamab (CAR 3.6 and 3) was evaluated in 2 studies with Sprague Dawley rats given a single intrathecal injection, and in 1 study with tumor-bearing athymic nude mice given a single IV injection of Lu-DTPA-omburtamab (CAR 3). The compound in these 3 studies was comparable to the clinical formulation (i.e., CAR  $\approx$  3).

Lu-DTPA-omburtamab concentration was significantly greater than the I-omburtamab concentration in the bone (1, 48, 144, and 192 hours), kidneys (48 and 192 hours), liver (all timepoints), and cervical spine (24, 48, 144, and 192 hours). Lu-DTPA-omburtamab concentration was significantly lower than I-omburtamab concentration in the cervical spine and upper thoracic spine at 1 hour and the lumbar spine at 5 hours. After 24 hours, the only region with Lu-DTPA-omburtamab concentration that was lower than the I-omburtamab concentration was the heart. Lu-DTPA-omburtamab gamma counts at 192 hours were generally increased compared to I-omburtamab. The liver, cervical lymph nodes, and spleen had the highest concentrations of Lu-DTPA-omburtamab at 192 hours. The highest concentrations of I-omburtamab at 192 hours were in the skin, liver, and cervical lymph nodes. Blood uptake for both labeled test articles was greatest at 24 hours.

In a second rat study, rats were given a single intrathecal injection of  $174.3 \pm 6.4$  or  $442.8 \pm 17.3 \mu\text{Ci}$  Lu-DTPA-omburtamab (CAR 3) or  $451 \pm 37.6 \mu\text{Ci}$  I-omburtamab. Biodistribution was evaluated up to 288 hours post dose. The highest levels of radioactivity were seen with the high dose of Lu-DTPA-omburtamab within the vertebral canal and brain at 1 hour post dose with subsequent clearance of radiopharmaceutical from these regions by 24 hours. At 24 hours and later, the highest radioactivity was in the liver and the deep and superficial cervical lymph nodes. Relatively little radioactivity was observed in the heart, lungs, spleen, kidneys, and humerus. Distribution of radioactivity over time following administration of the low dose was similar to high dose of Lu-DTPA-omburtamab.

Biodistribution was evaluated for up to 120 hours post dose and gamma counting was conducted at 120 hours post dose in male and female athymic nude mice bearing DAOY xenografts. Compared to I-omburtamab, Lu-DTPA-omburtamab accumulated 2-fold more in tumor relative to blood, and 2-fold less relative to liver. *In vivo* concentrations of Lu-DTPA-omburtamab were significantly ( $p < 0.05$ ) higher in tumor, blood, liver, lung, spleen, kidney, bladder, muscle, and bone at 120 hours post dose compared to I-omburtamab. *Ex vivo* concentrations of Lu-DTPA-omburtamab at 120 hours post dose were significantly ( $p < 0.05$ ) higher in the tumor, liver, spleen, kidney, and bone compared to I-omburtamab.

#### **1.2.4.1. Dosimetry**

The biodistribution data extrapolated from the SPECT/CT images were used as the input for dosimetry analysis (i.e., percentage injected dose per gram in key organs of interest over time) to generate estimates for 5-year-old (19 kg) humans. The 3 organs with the highest absorbed doses, the liver, heart wall, and kidneys, were the same for both test agents, albeit with different rank orders, and the effective doses were similar for the 2 test articles. The absorbed doses were higher in the liver and lower in the heart wall and kidneys with Lu-DTPA-omburtamab than I-omburtamab. Estimated absorbed doses for 5-year-olds are shown in [Table 1](#).

**Table 1: Estimated Absorbed Doses for a 5-year-old Human (19 kg)**

Target Organ	mGy/MBq		mGy/mCi		cGy per 25 mCi (1 dose)		cGy per 10 mCi (1 dose)		cGy per 10 mCi (2 dose)	
	Male	Female	Male	Female	Male	Female	Male	Female	Male	Female
Adrenals	0.48	0.48	17.86	17.63	44.65	44.08	17.86	17.63	35.72	35.26
Brain	0.31	0.34	11.49	12.70	28.72	31.76	11.49	12.70	22.976	25.41
Breasts	-	-	-	-	-	-	-	-	-	-
Esophagus	0.44	0.44	16.41	16.38	41.02	40.95	16.41	16.38	32.82	32.76
Eyes	0.42	0.41	15.53	15.26	38.83	38.16	15.53	15.26	31.06	30.53
Gallbladder Wall	0.50	0.46	18.40	17.05	45.99	42.63	18.40	17.05	36.79	34.10
Heart Wall	1.03	1.02	38.02	37.68	95.06	94.21	38.02	37.68	76.05	75.37
Kidneys	1.20	1.20	44.40	44.40	111.00	111.00	44.40	44.40	88.80	88.80
Left colon	0.44	0.43	16.26	15.97	40.65	39.93	16.26	15.97	32.52	31.94
Liver	3.12	3.12	115.50	115.50	288.76	288.76	115.50	115.50	231.01	231.01
Lungs	0.44	0.43	16.21	16.01	40.52	40.02	16.21	16.01	32.42	32.02
Osteogenic Cells	1.90	1.88	70.36	69.38	175.90	173.44	70.36	69.38	140.72	138.75
Ovaries	-	0.43	-	15.82	-	39.54	-	15.82	-	31.63
Pancreas	0.45	0.46	16.55	17.13	41.36	42.83	16.54	17.13	33.09	34.26
Prostate	0.42	-	15.66	-	39.16	-	15.66	-	31.33	-
Rectum	0.43	0.42	16.05	15.71	40.13	39.27	16.05	15.71	32.10	31.42
Red Marrow	0.62	0.60	22.91	22.36	57.27	55.90	22.91	22.36	45.82	44.72
Right colon	0.44	0.44	16.45	16.27	41.13	40.67	16.45	16.27	32.90	32.54
Salivary Glands	0.43	0.42	15.77	15.53	39.44	38.82	15.78	15.53	31.55	31.06
Small Intestine	0.44	0.43	16.21	16.01	40.52	40.04	16.21	16.02	32.42	32.03
Spleen	0.43	0.43	15.98	15.89	39.96	39.71	15.98	15.88	31.97	31.77
Stomach Wall	0.44	0.43	16.25	16.04	40.62	40.10	16.25	16.04	32.50	32.08
Testes	0.41	-	15.23	-	38.08	-	15.23	-	30.46	-
Thymus	0.43	0.43	15.95	15.73	39.87	39.31	15.95	15.72	31.90	31.45
Thyroid	0.42	0.42	15.69	15.66	39.22	39.16	15.69	15.66	31.38	31.33
Urinary Bladder Wall	0.43	0.42	15.97	15.61	39.93	39.02	15.97	15.61	31.94	31.22
Uterus	-	0.43	-	15.85	-	39.62	-	15.85	-	31.70
Total Body	0.58	0.58	21.56	21.55	53.91	53.88	21.56	21.55	43.13	43.10

### 1.3. Benefit-risk Assessment

Medulloblastoma is a disease associated with significant mortality and morbidity for which there is a large unmet need for effective treatments with less neurocognitive toxicity.

Lutetium-177 radiolabeled pharmaceuticals are currently approved (Lutathera) and being evaluated for treatment of multiple cancer indications, and I-omburtamab has known antitumor activity in animal models and in humans. Given the biodistribution, binding data, tumor uptake, and dosimetry data collected, it is reasonable to predict that

Lu-DTPA-omburtamab will have similar therapeutic potential and that 10 mCi is an acceptable starting dose in human (Section 3.3.3). In a rodent model, higher residence times in the brain are associated with greater tumor uptake with Lu-DTPA-omburtamab than with I-omburtamab. However, for every organ, except liver, Lu-DTPA-omburtamab showed lower absorbed doses (estimated by scaling to effective doses of 0.19 versus 0.28 mGy/MBq in females weighing 60 kg) suggesting greater tolerance for higher doses when administered into the CNS compartment. Based on dosimetry, 10 mCi I-omburtamab administered to a 10-kg child would deliver 14.4 cGy to the brain while 10 mCi of Lu-DTPA-omburtamab would deliver 13.2 cGy. For comparison, data published by Kramer et al. 2015 indicated that the mean CSF absorbed dose in patients receiving I-omburtamab was 0.60 Gy/mCi (0.17 to 2.07 Gy/mCi) and was well tolerated, even for patients who had received prior external beam craniospinal irradiation (in some cases twice) and a boost to the primary site (i.e., in total up to 28 × 2 and 24 Gy, respectively). The clinical efficacy and safety of direct infusion of I-conjugated antibodies (i.e., anti-B7-H3 and anti-GD2) into the CSF via an indwelling catheter (e.g., Ommaya catheter) has been demonstrated (Section 1.2.1). The conjugation of lutetium-177 with omburtamab allows for selectively targeting B7-H3, shown to be expressed on tumor cells and minimally in normal tissues. Preliminary findings suggest acceptable safety of I-omburtamab against recurrent/relapsed medulloblastoma and of I-3F8 (anti-GD2) against medulloblastoma. Taken together, the information supports the safety of intracerebroventricular administration of Lu-DTPA-omburtamab for the treatment of recurrent or refractory medulloblastoma in pediatric and adolescent patients.

For more detailed information about the known and expected benefits and risks and reasonably expected AEs of Lu-DTPA-omburtamab, please refer to the Investigator's Brochure.

## 2. OBJECTIVES AND ENDPOINTS

### 2.1. Objectives

#### 2.1.1. Primary Objectives

The primary objective of Part 1 (dose-escalation phase) of this trial is to explore the tolerability of up to 2 cycles of intracerebroventricular Lu-DTPA-omburtamab treatment in pediatric and adolescent patients with recurrent or refractory medulloblastoma. The MTD and/or the RP2D for Part 2 will be determined.

The primary objective of Part 2 (cohort-expansion phase) of this trial is to establish a safety profile of repeated dosing of Lu-DTPA-omburtamab in pediatric and adolescent patients with recurrent or refractory medulloblastoma.

#### 2.1.2. Secondary Objectives

The secondary objectives of Part 1 (dose-escalation phase) are:

- to evaluate the absorbed radiation doses to CSF and blood of Lu-DTPA-omburtamab after intracerebroventricular administration
- to evaluate organ dosimetry of Lu-DTPA-omburtamab
- to evaluate the PK profile of Lu-DTPA-omburtamab

The secondary objectives of Part 2 (cohort-expansion phase) are:

- to evaluate the PK profile of Lu-DTPA-omburtamab
- to evaluate the investigator-assessed response
- to evaluate the investigator-assessed DoR
- to evaluate PFS
- to evaluate OS.

### 2.2. Endpoints

#### 2.2.1. Primary Endpoints

The primary endpoint of Part 1 is number of DLTs.

The primary endpoint of Part 2 is number and severity of TEAEs.

## 2.2.2. Secondary Endpoints

### 2.2.2.1. *Part 1*

- Lutetium-177 activity in blood and CSF including derivation of best-fit uptake and/or clearance parameters (maximum count, elimination half-life) of time-activity curves and residence times (i.e., cumulated activity in  $\mu\text{Ci}\cdot\text{h/g}$ ).
- Whole-body, organ, blood, and CSF radiation dosimetry.
- PK profile of Lu-DTPA-omburtamab in serum and CSF.

### 2.2.2.2. *Part 2*

- PK profile of Lu-DTPA-omburtamab in blood and CSF.
- Response, as defined by the RAPNO criteria (as determined from MRI assessments, neurological examination, and CSF cytology).
  - ORR, calculated as the proportion of all evaluable patients achieving a response (PR or CR) as best overall response at end of Cycle 1 and Cycle 3, EOT Visit, and at each Follow-up Visit.
- Investigator-assessed DoR, defined as the time from first response (CR or PR) to progression.
- PFS, defined as the time from first treatment to date of leptomeningeal progression or death from any cause, whichever comes first.
- OS defined as the time from first treatment to date of death.

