###### ***4.3.2.1. Discontinuation of Trial Treatment***

Patients may withdraw from the trial treatment at any time at his/her own request or may be discontinued from trial treatment at any time at the discretion of the investigator for safety, behavioral, or administrative reasons. If the patient withdraws consent for disclosure of future information, the sponsor may retain and continue to use any data collected before such a withdrawal of consent. Additionally, patients may request destruction of any samples taken and not tested, and the investigator must document this in the site trial records. Refer to the Schedule of Assessments ([Appendix 3](#)) for data to be collected at the time of treatment discontinuation (EOT visit) and follow-up and for any further evaluations that need to be completed.

The patient must be permanently discontinued from treatment if any of the following occur:

- After receiving the dosimetry dose only, Grade 3 or 4 non-hematologic AE (including an AE considered to be a Grade 3 or 4 nervous system disorder; see [Section 7.1.5](#))
- DLT occurring before the end of Cycle 1 in each dose level in Part 1
- Grade 4 infusion-related reaction/anaphylaxis, or Grade 3 infusion-related reactions (excluding fever and Grade 3 abnormal laboratory values) that do not resolve to Grade  $\leq$  1 within 5 days of onset

- Grade 4 neurological AE
- Development of obstructive or symptomatic communicating hydrocephalus
- Grade 4 treatment-related AEs (excluding infusion-related fever, and non-life-threatening laboratory values)
- Disease progression before Cycle 2 in Part 1 or Cycle 5 in Part 2
- Any medical or safety reason, in the opinion of the investigator or sponsor
- Chemical meningitis (symptoms of clinical meningitis but cultures for infectious agents were negative) in which either: a) event is non-responsive to IV steroids, b) radiologic or operative intervention was indicated, or c) focal neurologic deficit was present
- The patient receives prohibited therapy and/or undergoes procedures during the trial that, in the opinion of the investigator, warrant treatment discontinuation
- Patient decision
- Pregnancy.

A patient who is discontinued from treatment, but for whom consent is not withdrawn, shall continue to be followed for the entire trial period.

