#### **4.3.5. *Follow-up of Patients Discontinued from Trial Treatment or from the Trial***

A patient discontinued from treatment should as soon as possible attend the EOT Visit, and be followed at all scheduled Follow-up Visits (Part 2) and for post-trial monitoring of secondary malignancies at least 10 years after end of trial, or until death, if sooner ([Appendix 3](#)).

The investigator should:

- Ensure the safety of the patient. Follow any SAE and Grade 3 or higher non-serious AEs that are considered treatment related and still ongoing after withdrawal until the event has been resolved or the investigator assesses the SAE as being chronic or stable.
- Offer the best possible treatment outside of the trial based on clinical practice at the investigational site.

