### 6.1. Permitted Concomitant Therapy

Any treatment needed for patient wellbeing (including supportive care) that will not interfere with IMP administration may be given at the discretion of the investigator. Additional anti-cancer and supportive care treatments are allowed after the EOT Visit. If an MRI is scheduled at that visit, the MRI should be completed before starting the additional treatments. Medical marijuana is permitted if the patient was receiving this therapy prior to signing the ICF.

After discontinuation of the IMP, any treatment deemed safe and justified by the investigator can be administered according to clinical practice and at the discretion of the investigator.

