### 6.2. Prohibited Concomitant Therapy

The following therapies are prohibited within 3 weeks prior to the first dose and until completion of the EOT Visit:

- Additional cytotoxic anti-cancer therapy.
- Any other IMP.
- Any live viral vaccines.
- Herbal medications with known risk of hepatotoxicity.

The following is prohibited in Part 1 Cycle 1 within 1 week prior to first IMP administration and until 5 weeks after:

- Additional hematological support.

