### 7.3.2. Response Evaluation, Overall Response Rate, and Duration of Response

Response, as defined by the RAPNO criteria (Warren et al. 2018; see Appendix 6) will be assessed in Part 1 at the EOT Visit. In Part 2, response will be assessed at end of Cycle 1 and Cycle 3, EOT Visit, then 26, 39, and 52 weeks post first dose, followed by 78 and 104 weeks post first dose of Lu-DTPA-omburtamab. Notably, objective response and stable disease requires that all criteria are met, while progression is defined when any of the PD criteria are met.

The ORR will be calculated from baseline MRI scans and from scans after the dosing of Lu-DTPA-omburtamab using 2 methods: firstly, by considering MRI data, neurological examination, and CSF cytology data together (RAPNO criteria); secondly, by considering CSF cytology data only. ORR will be defined as the proportion of all evaluable patients achieving a CR or PR as best overall response at the time of assessment.

Investigator-assessed DoR (Part 2) is defined as the time from response (CR or PR) to progression. Patients without any sign of progression will be censored at the date of their last PFS assessment.

In Part 1 and Part 2, the baseline CSF cytology assessment must be completed within 3 weeks prior to the first Lu-DTPA-omburtamab treatment dose infusion. Cerebrospinal fluid cytology should be assessed as positive/negative. Cerebrospinal fluid cytology will be assessed in Part 1 at screening, the EOT Visit, and in Part 2 at screening, end of Cycle 1 and Cycle 3, EOT Visit, and at each Follow-up Visit.

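### Part 2 ORR and DoR have no cut-off at progression or new anti-cancer therapy, and ORR is defined on an undefined evaluable set although Section 8 requires the FAS

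*Combined protocol and SAP*

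**What the plan says.** **Response window.** Section 2.2.2.2 defines Part 2 ORR as the share of evaluable patients with a CR or PR "as best overall response at end of Cycle 1 and Cycle 3, EOT Visit, and at each Follow-up Visit". Section 7.3.2 gives the follow-up times as weeks 26, 39, 52, 78 and 104 after first dose and words the endpoint as "best overall response at the time of assessment". Section 8.3 places the full efficacy analysis at the last patient's week 52; the week-104 update concerns survival.

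**Later therapy.** Section 6.1 states: "Additional anti-cancer and supportive care treatments are allowed after the EOT Visit". An MRI scheduled at the EOT Visit is protected, since "the MRI should be completed before starting the additional treatments". Section 6.1 also says that after the study drug is stopped "any treatment deemed safe and justified by the investigator can be administered according to clinical practice". The anti-cancer options that Section 6.2 bars until EOT are "Additional cytotoxic anti-cancer therapy" and other investigational products.

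**Follow-up.** Section 4.3.2.1 requires treatment to stop for progression before Cycle 5 and adds: "A patient who is discontinued from treatment, but for whom consent is not withdrawn, shall continue to be followed for the entire trial period".

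**DoR.** Section 7.3.2 runs DoR from response to progression and censors patients without progression at their last PFS assessment.

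**Denominator.** The ORR definitions (synopsis, 2.2.2.2, 7.3.2) use evaluable patients. Section 8.1 assumes 20 of 24 are evaluable and gives a 9% lower limit for 5 of 20. Evaluability for response is not among the analysis sets in Section 8.2. Sections 8.2 and 8.4 assign every efficacy endpoint to the FAS, that is, all dosed patients.

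**The concern.** Part 2 is a single-arm study. Its ORR and DoR can be read as activity of the study drug only if responses, and time in response, that arise under another treatment are set apart. As written, a patient who stops the drug, starts something else and shrinks at week 39 is a responder. A responder who starts other therapy without progressing continues to accrue duration. Patients stopped for progression remain under assessment, and they are plausibly the ones most likely to receive another treatment.

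The denominator problem does not depend on later therapy. Two instructions in the same document give different ORRs from the same data, and the set used in the endpoint definition has no membership rule. In an open-label trial that leaves a choice that could be made after the responses are known.

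**Working it through.** **1. Search for a cut-off.** The places where one would sit are the synopsis efficacy and statistical text, Sections 2.2.2.2, 7.3.1, 7.3.2, 8.3 and 8.4.1, and Appendix 6. None ends best overall response at progression or new therapy, and none censors DoR or PFS at new therapy.

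**2. Visits that can follow EOT.** Inputs: dosing on Days 1, 36, 71, 106 and 141 (Table 8, footnote 1); EOT Visit 5 to 6 weeks after last dose (4.3.2); Follow-up Visits at weeks 26, 39 and 52, each ±2 weeks; an extra visit with MRI at week 13 if the drug is discontinued after Cycle 1 (Table 8, footnote 2). EOT week = (last dose day − 1)/7 + 5 to 6.

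| Cycles received | EOT (weeks) | Visits to week 52 that can follow EOT |
|---|---|---|
| 1 | 5–6 | 13, 26, 39, 52 (four) |
| 2 | 10–11 | 26, 39, 52 (three) |
| 3 | 15–16 | 26, 39, 52 (three) |
| 4 | 20–21 | 26, 39, 52 (three) |
| 5 | 25–26 | 39, 52 (two) |

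One 8-week delay (5.3.1) with four cycles moves EOT to weeks 28–29, at or past the end of the week-26 window (24 to 28), which leaves two visits. With five cycles it moves EOT to weeks 33–34, still before week 39, so the count stays at two. Earlier-enrolled patients could also contribute week 78 or 104.

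**3. Response after progression.** In Appendix 6, PR is measured against baseline and PD against the smallest measurement. Take a lesion sum of 100 at baseline. A rise to 100 × 1.25 = 125 is PD. A later fall to 100 × 0.5 = 50, sustained for 4 weeks, meets the PR lesion criterion.

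**4. The plan's own precision figure.** The Clopper-Pearson lower limit is the 2.5% quantile of Beta(x, n − x + 1); the upper limit is the 97.5% quantile of Beta(x + 1, n − x).

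- 5/20 = 25.0%: 8.66% to 49.10%. The stated 9% is reproduced.
- 5/24 = 20.8%: 7.13% to 42.15%.
- 6/24 = 25.0%: 9.77% to 46.71%.

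For the same five responders, moving to the FAS lowers the estimate by 25.0 − 20.8 = 4.2 points and the lower limit by 8.66 − 7.13 = about 1.5 points.

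**5. Possible size of the window effect.** The documents give no count of responses under later therapy. Assume that 1, 2 or 3 of five responses were of that kind. Excluding them on the FAS gives 4/24 = 16.7% (4.7% to 37.4%), 3/24 = 12.5% (2.7% to 32.4%) or 2/24 = 8.3% (1.0% to 27.0%).

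**6. What a cut-off does to confirmation.** Appendix 6 requires an MRI response to last 4 weeks (28 days). After one cycle the scans fall at Day 29 and at EOT, Days 36 to 43, so 7 to 14 days apart. Using both ±4-day windows, the longest gap is Day 25 to Day 47, or 22 days. After three cycles, a response first seen at Day 99 meets EOT at Days 106 to 113, the same gap. Any response first seen at EOT needs a later scan. A strict cut-off can therefore leave some true drug responses unconfirmed.

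**The case against.** - **Following patients regardless of later therapy is a recognised strategy.** It is, but the plan never states that choice. It remains useful as a sensitivity analysis.
- **Appendix 6 already blocks response after progression.** It does so in part: for PR, a negative spine MRI or cytology must stay negative, nonmeasurable disease must not progress, and there must be no new extra-CNS site. It does not block a PR after growth of measurable lesions, or after clinical deterioration that later improves.
- **EOT responses are protected.** The EOT MRI is, by the sequencing rule in Section 6.1. The protection is incomplete because Section 6.1 also permits treatment once the drug is stopped, while Section 6.2 bars some therapies until EOT is completed. Those passages need reconciling. So do the EOT timing in Section 4.3.2 and Section 4.3.5, which says: "A patient discontinued from treatment should as soon as possible attend the EOT Visit".
- **ORR may be reported by visit.** The wording allows that, and the values at Cycles 1 and 3 and EOT would then be largely separable. The follow-up values would not.
- **A cut-off biases the other way.** This stands (working, step 6), and the fix has to deal with it.
- **The effect may be small and the endpoints are secondary.** This also stands. There is no test or success threshold, and Section 3.2 says there is no effective salvage treatment.

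A reader might go further and infer that the cytology-only ORR must be redefined on patients positive at baseline. Inclusion criterion 4 does admit cytology-negative patients, who cannot convert. But the documents do not give the number positive, Section 8.4 assigns the FAS, and a new responder rule would be a new endpoint definition. Only a supportive analysis is justified.

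**Conclusion.** The concern holds as a gap in the definitions. Following the plan as written can credit later treatment to the study drug in ORR and DoR, with two to four visits up to week 52 exposed, depending on cycles received. A reader might infer that the reported ORR will be materially inflated; the documents do not support that, because the number of responses under later therapy is unknown, and the 1-to-3 range above is an assumption.

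The denominator conflict is certain and modest: 25.0% with lower limit 8.7% on 20 patients, against 20.8% with lower limit 7.1% on 24, assuming the four non-evaluable patients count as non-responders. A reader might infer that the 9% is a miscalculation. It is correct for 5/20; it does not describe the FAS analysis that Section 8.4 specifies.

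The visit counts assume planned cycle days and EOT 5 to 6 weeks after last dose, with delays only where stated. The Part 2 primary endpoint is unaffected.

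**What to change.** 1. **Window.** Count toward best overall response only assessments up to the earlier of first RAPNO progression and the recorded start of new anti-cancer therapy. Censor DoR at the last assessment before new therapy. Report separately the responses left unconfirmed because new therapy began before the 4-week confirmation, and give ORR and DoR regardless of new therapy as a sensitivity analysis. Treat PFS in the same way as DoR, or state why not.
2. **Data check.** Section 6 collects start and end dates for medications, and Table 8 (footnote 5) keeps anti-cancer therapy in follow-up. Confirm that this record includes dates of radiotherapy and surgery.
3. **Denominator.** Use the FAS for the RAPNO ORR, as Section 8.4 states, with patients lacking a post-baseline assessment counted as non-responders. Define the evaluable set and keep it as supportive.
4. **Precision.** Restate Section 8.1 for 24 patients: 6/24 = 25%, lower limit 9.8%; 5/24 = 20.8%, lower limit 7.1%.
5. **Cytology.** As a supportive analysis only, also report the cytology-only ORR among patients positive at baseline.

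The cost is mainly wording, plus the data check. ORR will be lower and will lose some true drug responses that cannot be confirmed before new therapy; DoR will have more censoring. No change to permitted therapy is proposed.
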